### **(2) Dropout Criteria**

Participants lost to follow-up during the course of the clinical trial

Participants who voluntarily withdraw from the study due to lack of efficacy, adverse reactions, or other reasons.

### **(3) Termination Criteria**

Termination of the trial is decided by the participants and investigators when severe adverse reactions occur during the treatment process.

Significant protocol errors or deviations occur during the trial, making it difficult to evaluate clinical efficacy.

Participants develop other diseases or serious complications during the treatment period, requiring treatment or rescue measures that may affect the study protocol.

### **(4) Withdrawal Criteria:**

Participants request to withdraw from the clinical research.

Inability to complete the required assessments, resulting in data collection being compromised.

Participants receive unauthorized additional treatment during the study period.

Participants develop other diseases or serious complications during the treatment period, requiring treatment or rescue measures that may affect the study protocol.

## **Test grouping**

Patients with aMCI will be randomly allocated (1:1) to groups receiving either ccPAS or sham stimulation by personnel external to the clinical team using a computer-based algorithm.

## **Research process**

This study is mainly divided into three parts. First, identify the stimulation

---

targets related to long-term delayed recall; Second, intervene the stimulation target and observe the effect in patients with aMCI; Third, explore the relationship between the clinical efficacy and function of the stimulated brain region. Specifically, it is divided into the following six points: 1. In 21 healthy controls, the “cortex-hippocampus” network with white matter fiber connection will be identified based on probabilistic fiber tracking and segmentation techniques; 2. In the white matter based “cortex-hippocampus” network, identify the long-term delayed recall related to “cortex-hippocampus” functional connectivity in 42 patients with aMCI, and select the most relevant functional connectivity that TMS can stimulate as the stimulation target. 3. 42 patients with aMCI will be randomly divided into two groups (treatment group and sham stimulation group), and the stimulation targets on individual space will be calculated in each subject. 4. The TMS protocol and the sham stimulation protocol will be implemented in patients with aMCI. 5. The changes of cognitive function between the sham stimulation group and the treatment group before and after intervention will be compared. 6. The changes of fMRI between the sham stimulation group and the treatment group before and after intervention will be compared, as well as the impact of the changes on cognitive function.

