### **ccPAS Procedure**

Treatment will be delivered with a MagPro X100 stimulator equipped with the B70 fluid-cooled coil (MagVenture). The maximum surface magnetic field intensity of the coil is 4.2T. All patients will receive 10 interventions (5 times a week for two weeks). Each patient’s resting motor threshold (RMT) will be determined in accordance with standard clinical practice.

**Treatment group:** two B70 fluid-cooled coils will be needed for the ccPAS in left prefrontal lobe and left precuneus. The ccPAS consisted of 5-Hz stimulation and a total of 900 pairs pulses, the interval of each pair stimulation at two stimulation targets is 2ms. First, 80% RMT will be given to the left prefrontal lobe, and then 120% RMT will be given to the left precuneus. Five times a week for two consecutive weeks.

---

**Sham stimulation group:** the two coils will be placed vertically on the scalp of the patients, and the stimulation parameters will be the same as those in the treatment group. The sound generated by the coil simulating, and the method has virtually no effect on the cerebral cortex. Other parts are the same as the treatment group.

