## Statistical analysis

SPSS 21.0 (SPSS Inc., Chicago, Illinois) software will be used for statistical analysis in clinical data. The statistical description of measurement data is expressed by mean  $\pm$  standard deviation. The comparison of the two groups of mean: when it conforms to the normal distribution and homogeneity test of variance, the independent sample t test is used.

The stimulation targets related to long-term delayed recall will be identified by analyzing the relationship between FC of “cortex-hippocampus” circuit and AVLT long delayed memory performance in aMCI patients. Using the left hippocampus as the seed point, ROI based FC analysis to the cortical brain area of the “cortex-hippocampus” network will be calculated. A generalized linear model will be constructed with AVLT\_N5 score as dependent variable and every FC value of left “hippocampus-cortex” network as independent variable.

The repeated measurement ANOVA will be performed in comparison between the treatment group and sham stimulation group before and after treatment, the test of intra subject effect will be corrected by Greenhouse-Geisser, and the post test will be performed by LSD method. Effect sizes (Cohen’s d) will be interpreted as small = 0.2, medium = 0.5, large = 0.8. Non parametric test shall be adopted when it does not

---

conform to normal distribution or homogeneity of variance. The counting data will be expressed by frequency/rate, and the comparison between the two groups will be made by chi square test or Fisher exact probability method. The  $p < 0.05$  (two-sided) indicates significant statistical difference. GraphPad Prism 6 will be used for drawing.

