The statistical analysis of magnetic resonance data will be carried out using Matlab2013b, SPM12, GRETNA and the Resting State fMRI Data Analysis Toolkit (REST version 1.8). The flexible factorial of the second order analysis will be used to design the statistical matrix, and the three factors of subjects, grouping and time are set, in which grouping and time are fixed factors, and the number of subjects is random factors, and then the main effect and grouping $\times$  the time interaction matrix are set respectively for statistical analysis, and then post hoc analysis will be done. The results will be reported using bspmview software, and the names of brain regions will be referred to AAL template. BrainNetView and GraphPad Prism 6 are used for drawing. For correlation analysis, a generalized linear model will be fitted with the delta AVLT\_N5 as the dependent variable and the delta FC value between left hippocampus and left precuneus as independent variables, using age and years of education as covariates.

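### The protocol both plans to select the stimulation target from the 42 trial patients and already names it, and its selection model omits the age and education terms that it uses elsewhere

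*Protocol*

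**What the plan says.** **Target to be found.** Protocol, Research process, makes target identification the first of three parts. Step 1 defines a cortex–hippocampus network by fibre tracking in 21 healthy controls. Step 2 looks within that network for recall-related "functional connectivity in 42 patients with aMCI" and will "select the most relevant functional connectivity that TMS can stimulate as the stimulation target". Step 3 randomises the same 42 patients. Statistical analysis repeats the plan in the future tense: "The stimulation targets related to long-term delayed recall will be identified by analyzing the relationship between FC of" the cortex–hippocampus circuit and AVLT long-delayed recall. The seed is the left hippocampus. The model is a generalized linear model with the AVLT_N5 "score as dependent variable and every FC value of left" hippocampus–cortex network as independent variable. No covariates are named.

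**Target already named.** Protocol, ccPAS Procedure, Treatment group, says "two B70 fluid-cooled coils will be needed for the ccPAS in left prefrontal lobe and left precuneus". The magnetic resonance part of Statistical analysis regresses the change in AVLT_N5 on "the delta FC value between left hippocampus and left precuneus as independent variables, using age and years of education as covariates".

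**The concern.** The two sets of statements describe different studies. In one, part 1 is a search whose result decides where patients are stimulated. In the other, the sites were known when the protocol was written and part 1 can only describe them. The protocol does not say which applies, what happens if another connection ranks first, or where the named sites come from. A search seeded on the left hippocampus returns hippocampus–cortex connections, and the text does not explain how a left prefrontal site follows from it.

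Two analytic matters depend on this part. The selection model has no age or education term, although patients span 50–80 years and the later connectivity–recall model adjusts for both. And if step 2 really selects, the baseline values that pick the connection reappear inside both change scores of that later model.

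At stake are the claim that the target is recall-related and the exploratory link between change in connectivity and change in recall.

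**Working it through.** **1. Passages side by side**

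| Place in the protocol | Status of the target |
|---|---|
| Research process, step 2 | To be selected from 42 patients, before randomisation |
| Statistical analysis, target paragraph | To be identified; left-hippocampus seed |
| ccPAS Procedure, Treatment group | Named: left prefrontal lobe, left precuneus |
| Statistical analysis, magnetic resonance | Named: left hippocampus–left precuneus |

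The first two rows and the last two cannot both describe the state of knowledge before step 2.

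**2. The plan's own figure.** No figure is given for the search. The sample size concerns the treatment comparison. With difference 5.1 − 2.6 = 2.5, SD 2.23, two-sided 0.05 and 90% power, the normal formula gives a total of 4 × (2.23 × (1.960 + 1.282) / 2.5)² = 33.4, against the stated 33. Then 33 / (1 − 0.20) = 41.25, rounded up to 42, if attrition is taken as 20% (assumed). The figure reproduces and is not in question here.

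**3. Age in the selection model.** Assume age correlates *a* with recall and *a* with one connection that has no direct link to recall. The unadjusted correlation is then a². By the Fisher transformation, z = atanh(a²) × √39, and the chance of p<0.05 is 1 − Φ(1.96 − z) + Φ(−1.96 − z).

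| a (assumed) | Spurious r | Chance of p<0.05, n = 42 |
|---|---|---|
| 0.3 | 0.09 | 9% |
| 0.4 | 0.16 | 17% |
| 0.5 | 0.25 | 36% |

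With age in the model, the direct association is zero and the rate returns to 5%.

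**4. What a ranking returns by chance.** The number of connections K is not stated, so it is assumed. With n = 42, |r| above 0.304 gives p<0.05. With no true association (4,000 simulated data sets), the median of the largest |r| is:

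| K | Independent | Correlated at 0.5 |
|---|---|---|
| 10 | 0.29 | 0.26 |
| 20 | 0.33 | 0.29 |
| 40 | 0.37 | 0.32 |

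A ranking always yields a top connection, and a chance one will often have a correlation close to or above the nominal threshold.

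**5. Reuse of the baselines, only if step 2 selects.** Simulation with n = 42, 6,000 replicates and no association at any time: pick the connection with the largest baseline |r|, then test change in connectivity against change in AVLT_N5. Assumptions: K = 10 to 40, reliability 0.3–0.5 for connectivity and 0.5–0.7 for AVLT_N5. Rejection at 5% nominal was 5.8% to 9.6%. With both baselines in the model it was 4.2% to 5.2%.

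**6. Cost in degrees of freedom.** With one connection per selection model, residual degrees of freedom fall from 42 − 2 = 40 to 38 when age and education enter. The change model already has three terms, so two baseline terms take it from 42 − 4 = 38 to 36, with all 42 patients analysed.

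**The case against.** **The complaints are partly alternatives.** If the sites were fixed beforehand, the search picked nothing, and neither chance selection nor reuse of baselines arises. The sample size section takes its figures from a preliminary study of the new treatment, which hints at an earlier target without saying so. This stands: those points are conditional. The contradiction and the missing covariates do not depend on it.

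**Multiplicity.** A reader might infer that the target is a chance pick, citing 1 − 0.95^K = 40%, 64% and 79% for K = 10, 20 and 30. The protocol does not support that. K is not stated, and the connections share one seed and are unlikely to be independent; at an assumed correlation of 0.5 the figure is about 29% for K = 10 and 42% for K = 20. The stated rule ranks connections by relevance and feasibility and has no p<0.05 gate, so error control would limit the claim about the chosen connection without changing the ranking. A correction rule may also sit in an unseen SAP. If the text means one joint model, the calculation does not apply and the problem is overfitting: with 20 connections, 42 − 21 = 21 residual degrees of freedom remain. Finally, the search is confined to the left-hippocampal seed and the network from the healthy controls; it does not cover every hippocampal connection.

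**Covariates.** Naming none does not exclude them. That is fair, but the protocol specifies them for its other connectivity–recall model, so leaving them out here is an inconsistency within the text.

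**Small consequence.** The inflation is modest, rests on assumed reliabilities, and affects an analysis that Outcome labels exploratory. This stands.

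**Conclusion.** The contradiction holds on the text alone, and an SAP cannot cure it, because both statements are in the protocol. It decides whether the trial may report a data-derived, recall-related target or only a description of one fixed beforehand. No view is taken on which site is right.

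The missing age and education terms are a real but smaller defect: about 9% to 36% false associations for an age-linked connection, under assumed correlations of 0.3 to 0.5. Reuse of the baselines matters only if step 2 selects, and then raises type I error to about 6–10% under the assumptions in the working.

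A reader might infer that the treatment effect itself is compromised. It is not: selection uses baseline data before allocation, and it does not differ by arm, so the randomised ccPAS–sham comparison stands. Only the target-identification claim and the exploratory connectivity–recall association are weakened.

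**What to change.** 1. Reconcile Research process and the target paragraph of Statistical analysis with ccPAS Procedure and the change model. State whether part 1 selects the target or describes one fixed beforehand. If it was fixed, give its source. In either case explain how the prefrontal site relates to a left-hippocampus-seeded search.
2. Add age and years of education to the AVLT_N5 selection model, and say whether connections are fitted one at a time or jointly.
3. If step 2 does select, report the selected association as exploratory, or with error control across the left-hippocampal connections searched. Add baseline connectivity and baseline AVLT_N5 to the change model.

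The cost is protocol wording and a short re-analysis. Age and education are already in the planned change model, so no new data are needed. Each model loses two degrees of freedom at n = 42, and fewer connections, or none, may reach significance.

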### **ccPAS Procedure**

Treatment will be delivered with a MagPro X100 stimulator equipped with the B70 fluid-cooled coil (MagVenture). The maximum surface magnetic field intensity of the coil is 4.2T. All patients will receive 10 interventions (5 times a week for two weeks). Each patient’s resting motor threshold (RMT) will be determined in accordance with standard clinical practice.

**Treatment group:** two B70 fluid-cooled coils will be needed for the ccPAS in left prefrontal lobe and left precuneus. The ccPAS consisted of 5-Hz stimulation and a total of 900 pairs pulses, the interval of each pair stimulation at two stimulation targets is 2ms. First, 80% RMT will be given to the left prefrontal lobe, and then 120% RMT will be given to the left precuneus. Five times a week for two consecutive weeks.

---

**Sham stimulation group:** the two coils will be placed vertically on the scalp of the patients, and the stimulation parameters will be the same as those in the treatment group. The sound generated by the coil simulating, and the method has virtually no effect on the cerebral cortex. Other parts are the same as the treatment group.

## Outcome

1. The primary outcome is change from baseline in long-term delayed recall performance (Delta AVLT\_N5) following the ccPAS intervention compared with the sham stimulation group.
2. Secondary outcome measures is also recorded as the primary outcome, included MMSE, other AVLT items, STT, SDMT, BNT, CFT. In exploratory analyses, we will assess the relationship of changes in cognitive performance and FC.

## Statistical analysis

SPSS 21.0 (SPSS Inc., Chicago, Illinois) software will be used for statistical analysis in clinical data. The statistical description of measurement data is expressed by mean  $\pm$  standard deviation. The comparison of the two groups of mean: when it conforms to the normal distribution and homogeneity test of variance, the independent sample t test is used.

The stimulation targets related to long-term delayed recall will be identified by analyzing the relationship between FC of “cortex-hippocampus” circuit and AVLT long delayed memory performance in aMCI patients. Using the left hippocampus as the seed point, ROI based FC analysis to the cortical brain area of the “cortex-hippocampus” network will be calculated. A generalized linear model will be constructed with AVLT\_N5 score as dependent variable and every FC value of left “hippocampus-cortex” network as independent variable.

The repeated measurement ANOVA will be performed in comparison between the treatment group and sham stimulation group before and after treatment, the test of intra subject effect will be corrected by Greenhouse-Geisser, and the post test will be performed by LSD method. Effect sizes (Cohen’s d) will be interpreted as small = 0.2, medium = 0.5, large = 0.8. Non parametric test shall be adopted when it does not

---

conform to normal distribution or homogeneity of variance. The counting data will be expressed by frequency/rate, and the comparison between the two groups will be made by chi square test or Fisher exact probability method. The  $p < 0.05$  (two-sided) indicates significant statistical difference. GraphPad Prism 6 will be used for drawing.

The statistical analysis of magnetic resonance data will be carried out using Matlab2013b, SPM12, GRETNA and the Resting State fMRI Data Analysis Toolkit (REST version 1.8). The flexible factorial of the second order analysis will be used to design the statistical matrix, and the three factors of subjects, grouping and time are set, in which grouping and time are fixed factors, and the number of subjects is random factors, and then the main effect and grouping $\times$  the time interaction matrix are set respectively for statistical analysis, and then post hoc analysis will be done. The results will be reported using bspmview software, and the names of brain regions will be referred to AAL template. BrainNetView and GraphPad Prism 6 are used for drawing. For correlation analysis, a generalized linear model will be fitted with the delta AVLT\_N5 as the dependent variable and the delta FC value between left hippocampus and left precuneus as independent variables, using age and years of education as covariates.

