### **Sample size calculation**

Sample size calculation was calculated based on long delay recall score as the main observation index. As this study adopts a new treatment method, sample size was acquired from our preliminary study. As a result, the mean (5.1) and standard deviation (2.23) after treatment, as well as the mean (2.6) after false stimulation, a minimum total sample size of 33 treatment-completers was required to achieve 90% power at  $\alpha=0.05$ . To account for attrition and ensure adequate power at 2 weeks after treatment, 42 participants need to be included, with 21 subjects in each group.

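### The repeated-measures ANOVA for AVLT_N5 is a change-score test without baseline adjustment: valid, but asymptotically never more precise than ANCOVA, with a gain of unknown and possibly small size

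*Protocol*

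**What the plan says.** The Outcome section defines the endpoint: "The primary outcome is change from baseline in long-term delayed recall performance" (Delta AVLT_N5), ccPAS against sham. For the comparison of arms over time, the Statistical analysis section says: "The repeated measurement ANOVA will be performed in comparison between the treatment group and sham stimulation group before and after treatment". It adds a Greenhouse-Geisser correction, LSD post hoc tests and a nonparametric fallback. The same section has a general rule for comparing two means: "when it conforms to the normal distribution and homogeneity test of variance, the independent sample t test is used".

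None of these analyses names a baseline covariate. Covariates appear only in the model relating change in AVLT_N5 to change in functional connectivity, and they are age and education. Baseline AVLT_N5 is available for every patient, because low long delayed recall is an entry requirement (Inclusion criteria) and because the change score needs it.

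The Sample size calculation section plans on "the mean (5.1) and standard deviation (2.23) after treatment, as well as the mean (2.6) after false stimulation" and concludes that "a minimum total sample size of 33 treatment-completers was required to achieve 90% power".

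**The concern.** A repeated-measures ANOVA on two time points subtracts the whole baseline score from the follow-up score. That is the best linear correction only if a patient who starts one point higher is expected to finish exactly one point higher. If the true slope differs from 1, the subtraction corrects too much or too little. The result is added noise and an estimate that moves with whatever baseline difference chance produces between two arms of 21. ANCOVA estimates the slope from the data instead.

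At stake are precision and robustness to chance imbalance in a small trial. The type I error rate is not at issue. Because the protocol itself fixes the unadjusted model, this is a stated choice and not a detail left open for a later plan.

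**Working it through.** **Inputs.** Means 5.1 and 2.6 (difference 2.5), SD 2.23, alpha 0.05, 90% power and 33 completers come from Sample size calculation. Two-sided testing comes from Statistical analysis, and 1:1 allocation from Test grouping. The protocol does not give the baseline to follow-up correlation (rho) or the ratio k of baseline SD to follow-up SD. Both are assumptions below. I take before and after treatment to mean one score each, and 2.23 to be the SD of the post-treatment score, as the protocol words it.

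**Step 1: the plan's own figure.** Total N = 4 × [2.23 × (1.960 + 1.282) / 2.5]² = 33.4, which agrees with the stated 33. Exact t-test power with 17 and 16 completers and SD 2.23 is 87.6%; 33 is a normal-approximation figure.

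**Step 2: what the ANOVA tests.** With two time points, the group-by-time F is the square of the t statistic on change, and the Greenhouse-Geisser correction has no effect.

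**Step 3: variances.** In units of the follow-up variance:
- change score: 1 + k² − 2·rho·k
- ANCOVA: 1 − rho²
- difference: (k − rho)², which is never negative and is zero when k = rho
- true baseline slope: rho/k

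**Step 4: equal SDs (k = 1).** The variance ratio reduces to (1 + rho)/2. Power is noncentral t, 17 and 16 completers, 31 df for change and 30 df for ANCOVA.

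| rho | ratio ANCOVA/change | reduction | power, change | power, ANCOVA |
|---|---|---|---|---|
| 0.3 | 0.65 | 35% | 75.0% | 90.4% |
| 0.5 | 0.75 | 25% | 87.6% | 94.9% |
| 0.7 | 0.85 | 15% | 98.0% | 99.2% |

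At rho 0.5 the change SD is 2.23 × √(2 × 0.5) = 2.23, so that row repeats the 87.6% of Step 1.

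**Step 5: baseline narrowed by selection.** Patients must score at least 1.0 SD below the age-matched mean, so k may be below 1. With k = 0.6:

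| rho | slope rho/k | ratio |
|---|---|---|
| 0.3 | 0.50 | 0.91/1.00 = 0.91 |
| 0.5 | 0.83 | 0.75/0.76 = 0.99 |
| 0.6 | 1.00 | 0.64/0.64 = 1.00 |
| 0.7 | 1.17 | 0.51/0.52 = 0.98 |

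Power at rho 0.5 is 94.7% (change) against 94.9% (ANCOVA).

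A second version takes a normal population cut at −1 SD, with the eligibility score serving as baseline. The retained baseline variance is 0.199 of the original, and the ratio is (1 − rho²)/[(1 − rho)² × 0.199 + 1 − rho²]. For unselected rho of 0.3, 0.5 and 0.7 it is 0.903, 0.938 and 0.966, reductions of about 10%, 6% and 3%. Power is 84.9% against 88.2%, 87.6% against 89.5%, and 91.7% against 92.5%.

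**Step 6: the cost of estimating the slope.** Simulation with 17 per arm and equal SDs gave ratios of 0.672, 0.775 and 0.880 where theory gives 0.65, 0.75 and 0.85, about 3 to 4% more variance for ANCOVA. Both estimators averaged 2.5, the true effect. Charging this cost brings ANCOVA power in Step 4 to 89.4%, 94.2% and 99.0%.

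**Step 7: chance imbalance.** The change-score and ANCOVA estimates differ by (1 − slope) × (baseline difference between arms). With baseline SD 2.23 the standard error of that difference is 2.23 × √(1/17 + 1/16) = 0.78. At slope 0.5, a one-standard-error imbalance moves the change-score estimate by 0.5 × 0.78 = 0.39 points, against a planned effect of 2.5. At k = 0.6 and rho 0.5 the shift is (1 − 0.83) × 0.6 × 0.78, about 0.08.

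**The case against.** The strongest reply is that the large gains assume equal SDs, whereas the entry criterion selects on the outcome variable and should narrow the baseline. That stands. Under narrowing the asymptotic gain is 0 to 10%, and near slope 1 the cost in Step 6 can exceed it: at k = 0.6 and rho 0.5, the 94.2% power charged for the slope is slightly below the 94.7% of the change score. The advantage is therefore not guaranteed at this sample size, though the possible loss is small.

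Three stronger readings are tempting, and the protocol does not support them.

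- *The planned estimate is biased, in favour of the arm with the lower baseline.* Allocation is randomised, so the change-score comparison is unbiased with correct type I error. Any shift is conditional on the imbalance that happens to occur, and its direction depends on the slope: at k = 0.6 and rho 0.7 the slope is 1.17 and the change score under-corrects.
- *The primary analysis is an unadjusted t test.* The sentence stating that "the independent sample t test is used" is a general rule for two means and is not tied to the primary outcome. The before/after comparison is assigned to the ANOVA.
- *The analysis contradicts the endpoint.* It does not; a change-score test matches an endpoint defined as change.

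**Conclusion.** The point holds as one of efficiency and robustness. The protocol fixes an analysis equivalent to a change-score test, when the baseline needed for an asymptotically at least as precise analysis is already in hand. The variance reduction is 15 to 35% for rho 0.7 to 0.3 with equal SDs, and about 0 to 10% if selection narrows the baseline, before the small cost of estimating the slope. Neither rho nor the SD ratio is in the protocol, so no single value in that range should be presented as the loss.

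A reader might infer from the 75.0% and 87.6% figures that the trial is underpowered because of this choice. That does not follow: with equal SDs and rho 0.7 the change score has 98.0% power, and with k = 0.6 and rho 0.5 it has 94.7%. The conclusion rests on one score before and one after treatment, and on 2.23 being a post-treatment SD.

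**What to change.** In Statistical analysis, name the primary analysis of AVLT_N5 as an ANCOVA of the post-treatment score on arm with baseline AVLT_N5 as covariate. Using change as the dependent variable gives the same treatment estimate as long as baseline is in the model. Report the adjusted mean difference between arms with its 95% CI. Analyse the secondary cognitive scores in the same way, each with its own baseline, in place of the group-by-time test. State also what the nonparametric fallback means for this analysis, so that a failed assumption check does not remove the adjustment by default.

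The cost is one degree of freedom, a slightly larger standard error when the slope is close to 1 (about 3 to 4% in variance at 17 per arm), and a change of wording. No new data are needed, and the model is standard in the planned software. The sample size need not change for this reason.

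### Assumption checks on the trial data choose between a mean comparison and an unnamed non-parametric test for the primary change score, so the estimand is not fixed in advance

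*Protocol*

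**What the plan says.** Under Outcome, the protocol fixes the variable: "The primary outcome is change from baseline in long-term delayed recall performance", written Delta AVLT_N5, ccPAS against sham.

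Under Statistical analysis it gives two parametric routes and one fallback:

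- For two means: "when it conforms to the normal distribution and homogeneity test of variance, the independent sample t test is used".
- For the before/after comparison: "The repeated measurement ANOVA will be performed in comparison between the treatment group and sham stimulation group before and after treatment".
- Otherwise: "Non parametric test shall be adopted when it does not" "conform to normal distribution or homogeneity of variance".

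The section does not say which of the two parametric routes is primary. The fallback follows both and names no test. Neither parametric route uses the baseline score as a covariate.

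Under Sample size calculation, the planning figures are means: "the mean (5.1) and standard deviation (2.23) after treatment, as well as the mean (2.6) after false stimulation".

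**The concern.** The fallback is a stated rule, so an analysis plan that follows the protocol inherits it. Three things follow.

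1. The test that decides the trial is known only after the outcome data have been examined. With 21 patients per arm, the result of a normality or variance check is itself largely chance.
2. The two branches answer different questions. The t test and the ANOVA estimate a difference in mean change. A rank test addresses whether one arm tends to have larger values, and it has a shift interpretation only if the two distributions have the same shape.
3. Unequal variance is a trigger in its own right. That is the situation in which the shape assumption fails, so a rank test does not repair a comparison of means. Welch's test or a robust standard error does.

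At stake is whether the reported effect is the quantity on which the trial was sized.

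**Working it through.** **1. The plan's own figure.** The inputs from Sample size calculation are means 5.1 and 2.6 (difference 2.5), SD 2.23, alpha 0.05 (two-sided under Statistical analysis) and 90% power.

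n per arm = 2 × (1.960 + 1.282)² × 2.23² / 2.5² = 2 × 10.507 × 4.973 / 6.25 = 16.72, or 33.4 in total.

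This agrees with the stated 33 up to rounding; 17 per arm would be 34. Enrolling 42 allows for 1 − 33/42 = 21.4% attrition. The formula is the one for a difference in means, so the mean difference is the quantity that was powered.

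**2. How often the rule would switch.** The protocol gives no score range, no pre-post correlation and no pre-test. The assumptions were:

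- score 0-12, rounded and clipped at both ends;
- SD 2.23 before clipping, in both arms and at both visits;
- baseline mean before clipping 2.6 or 1.5;
- correlation 0.3, 0.5 or 0.7;
- Shapiro-Wilk in each arm and Levene between arms, each at 0.05;
- 21 per arm, 2,000 runs per scenario.

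Share of trials with at least one failed pre-test:

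- change score, baseline mean 2.6: 24-50%;
- change score, baseline mean 1.5: 34-69%;
- change score, normal data without a floor: 15%;
- raw baseline and post scores: 80% to nearly 100% with the floor, 22% without it.

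Repeat simulations of the same kind widen the range for the change score to 22-71%.

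**3. What the switch does to error and power.** Type I error of the whole procedure on change scores was 4.4-5.5% (4.6-5.9% in a repeat), against 3.4-5.3% for ANCOVA with conventional standard errors. Power at a 1.5-point effect (before clipping):

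| Baseline mean | Correlation | Pre-test fails | t test on change | Switching rule | ANCOVA |
|---|---|---|---|---|---|
| 2.6 | 0.3 | 27% | 42.0% | 41.8% | 58.3% |
| 2.6 | 0.5 | 31% | 54.4% | 53.2% | 64.9% |
| 2.6 | 0.7 | 48% | 74.0% | 72.7% | 79.4% |
| 1.5 | 0.3 | 35% | 44.4% | 43.8% | 56.4% |
| 1.5 | 0.5 | 45% | 52.0% | 52.1% | 61.8% |
| 1.5 | 0.7 | 64% | 73.4% | 73.0% | 75.8% |

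The switching rule stays within about 1 point of the t test. At the planned 2.5 points it has 87-99% power, against 95-99.6% for ANCOVA.

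**4. Where the ANCOVA gain comes from.** With equal SDs and no floor, the variance of the group difference is proportional to 2(1 − ρ) for change scores and to 1 − ρ² for ANCOVA. The ratio is (1 + ρ)/2, which is 0.65, 0.75 and 0.85 at ρ = 0.3, 0.5 and 0.7. The gain comes from adjusting for baseline and would be the same against an unswitched t test on change. HC3 standard errors give some of it back at this sample size: power at 1.5 points is then 53-77%, against 43-75% for the switching rule in the same simulation.

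**The case against.** The strongest reply is that the rule does little measurable damage. That stands. Type I error holds near 5%, and the rank test on change is within about 2 points of the t test in power. Which pre-test, threshold and rank test to use may also properly be left to a statistical analysis plan, so their absence is not held against the protocol. The rule itself is in the protocol, and that part of the point remains.

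A reader might infer more than the documents support:

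- **That the rank branch cannot address group-by-time.** With one pre and one post measurement, the group-by-time test is the two-sample test on change. A Mann-Whitney test on Delta AVLT_N5 is its rank counterpart and comes with a Hodges-Lehmann shift. Only a rank test on post scores alone would lose it, and the protocol does not say that this is intended.
- **That switching gives up a baseline adjustment.** Neither parametric branch has one, so nothing is lost at the switch. The ANCOVA gain is not a cost of the switch.
- **That floor scores make normality impossible for the primary variable.** A normal curve with mean 2.6 and SD 2.23 puts Φ(−2.6/2.23) = 12% of its mass below zero, and a bounded-score model (beta-binomial, 0-12) with that mean and SD fails Shapiro-Wilk in about 68% of samples of 21. Both figures describe raw scores, and they attach the SD given for the treated arm to the sham mean. A change score can be negative. The protocol mentions no floor; it is inferred from selection on low recall.
- **That a real effect would itself cause the switch.** This needs a mixture of responders and non-responders. If half of the ccPAS patients gained 5 points and half none, Levene's test on change would reject in 31-75% of simulated trials. No section of the protocol supports such a split, so this is an illustration only.

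**Conclusion.** The concern holds in a limited form. The protocol lets checks on the outcome data choose between a mean comparison and an unnamed non-parametric test for Delta AVLT_N5. It also sends unequal variances to the latter, although the trial was sized on a mean difference. The estimand is therefore not fixed in advance, and a change of branch would be an ordinary event: roughly 22-71% of trials if the change score is the variable checked. That range rests on the assumed 0-12 scale, the floor, the correlation of 0.3-0.7 and the choice of pre-tests, none of which the protocol gives. Even without a floor the rate is about 15%.

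There is no evidence of inflated type I error or of material power loss from the switch. The efficiency to be gained, 53-77% against 43-75% power at a 1.5-point effect, comes from baseline adjustment that every branch lacks. It is largest at low pre-post correlation and small at 0.7. The point is an improvement at no cost in patients, and it does not make the planned analysis invalid.

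**What to change.** In Statistical analysis, delete the normality/variance switch for the primary and secondary cognitive scores. Name one primary analysis that applies whatever the distribution looks like: ANCOVA of post-treatment AVLT_N5 on group and baseline AVLT_N5 with HC3 standard errors, reporting the adjusted mean difference and its 95% confidence interval. The group coefficient is the same whether the post score or Delta AVLT_N5 is the dependent variable, so the declared outcome is kept.

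Add one named sensitivity analysis on Delta AVLT_N5: Mann-Whitney with a Hodges-Lehmann shift, or a permutation test. Report it alongside the primary result; it should not replace it.

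The cost is a change of wording and one extra analysis. Baseline AVLT_N5 is already collected, and the sample size stays at 42.
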